9.2 Clinical Variables

9.2.1 CT Endpoints

The independent, blinded reviewer will perform computer assisted measurements in the FSO and frontal sinus outflow tract (FSOT) according to a validated protocol (See CP-00038).

Cross-sectional area of the FSO

The cross-sectional area within the mucosa and the bone at the location of the measured minimum diameter between 5 mm superior and 5 mm inferior to the ostium. It will be reported in mm² for the mucosa and bone for the left and right ostia separately. This measurement will be repeated at the location 5 mm superior and 5 mm inferior to the ostium.

FSO minimum diameter

The minimum diameter as output by the segmentation software at the FSO reference plane between the boundaries of the mucosa and bone, representing the pneumatized portion of the ostium (with mucosa as boundaries) or the pneumatized and mucosal portions of the ostium (with bone as boundaries). It will be reported in mm for the left and right ostia separately. This measurement will be repeated at the CT slice corresponding to the location 5 mm superior and 5 mm inferior to the ostium.

FSOT volume

The volume of the patent frontal sinus outflow tract (FSOT) between boundaries of the mucosa located 5 mm superior and 5 mm inferior to the ostium in the 3D volume segmentation of the FSOT. It will be reported in mm³ and measured separately for the left and right FSOT. This space

corresponds to the implant location. The measurements will be repeated for the volume of mucosal and patent FSOT (i.e., with bone as boundaries).

Zinreich's modified Lund-Mackay score

Each sinus is assigned a score based on the percentage of opacification from mucosal thickening as follows:

- 0: 0%
- 1: 1% to 25%
- 2: 26% to 50%
- 3: 51% to 75%
- 4: 76% to 99%
- 5: 100% or completely occluded

The ostiomeatal complex (OMC) is given a score of 0 if it is completely patent, 1 if it is partially obstructed, or 2 if it is completely obstructed. Similar to the Lund-Mackay system, each side is graded, and their sum is the total score out of maximum of 54.

Lund-Mackay score

For each of the frontal, anterior ethmoid, posterior ethmoid, maxillary, and sphenoid sinus, a value of 0 is assigned if the sinus is totally patent, 1 if it is partially opacified, or 2 if it is completely opacified. The OMC is scored either 0 or 2. The maximum score for each side is thus 12, with a total score determined out of 24 after summing both sides. The Lund-Mackay scores are evaluated by the independent, blinded reviewer and by clinical investigators.

9.2.2 Endoscopic Endpoints

Adhesion/scarring grade in the frontal recess/FSO and ethmoid sinus

Adhesion/scarring severity in the FSO is assessed on a 4-point scale as follows:

- 0: No visible granulation/scarring in the FSO
- 1: Minimal amount of granulation, scarring or contraction observed but not obstructing the FSO (intervention not warranted)
- 2: Moderate amount of obstructive granulation, scarring or contraction present in the FSO (intervention is warranted)
- 3: Significant amount of scarring or contraction causing obstruction of the FSO requiring intervention (likely to compromise patency if not removed)

Adhesion/scarring severity in the ethmoid sinus graded on a 5-point scale as follows:

- 0: None
- 1: Small but non-obstructing (no separation required)
- 2: Obstructing, but easily separated
- 3: Dense and obstructing, separation difficult
- 4: Severe: complete adhesion of the middle turbinate to the lateral nasal wall

Inflammation score in the frontal recess/FSO

For the purpose of the endoscopic scoring method in this study, the term inflammation is a global descriptor that includes erythema, edema and/or polypoid changes. The inflammation present in the frontal recess/FSO is estimated visually based on the endoscopic examination on a scale ranging from 0 (no visible inflammation) to 100 (severe inflammation) involving extensive erythema, edema, or polyposis.

Polypoid edema in the frontal recess/FSO

Polypoid edema in the frontal recess/FSO is assessed on a 4-point scale as follows:

- 0: Normal mucosa, no visible polyps/mucosal edema
- 1: Minimal amount of polyps/mucosal edema
- 2: Moderate amount of polyps/polypoid edema
- 3: Expanded amount of polyps/polypoid edema

Polyp grade in the ethmoid sinus

Polyps originating from the ethmoid sinus are assessed endoscopically and graded on an 8-point scale as follows:

- 0: No visible sinonasal polyps
- 1: Small amount of sinonasal polyps confined in middle meatus
- 1.5: Small amount of sinonasal polyps confined in middle meatus with expanded amount of polypoid edema obstructing $\geq 25\%$ of the ethmoid sinus cavity
- 2: Expanded amount of sinonasal polyps confined in middle meatus
- 2.5: Expanded amount of sinonasal polyps confined in middle meatus with expanded amount of polypoid edema obstructing $\geq 50\%$ of the ethmoid sinus cavity
- 3: Sinonasal polyps extending beyond middle meatus but not totally obstructing the nasal cavity
- 3.5: Sinonasal polyps extending beyond middle meatus with expanded amount of polypoid edema obstructing $\geq 75\%$ of the ethmoid sinus cavity

- 4: Sinonasal polyps completely obstructing the nasal cavity

9.2.3 Need for Post-operative Intervention

Need for post-operative intervention is determined by clinical investigators at Day 21, 45, 90, and 180 as follows:

- Repeat frontal BSD warranted or performed for restenosis/occlusion in the frontal recess/FSO; or
- Surgical intervention warranted or performed to debride obstructive adhesions/scarring or for restenosis/occlusion in the frontal recess/FSO; or
- Oral steroids warranted or prescribed to resolve recurrent edema in the frontal recess/FSO.

9.2.4 Patient-Reported Outcomes

9.2.4.1 SNOT-22 Questionnaire

The Sino-Nasal Outcome Test (SNOT-22) questionnaire is a validated, disease-specific, symptom-scoring instrument consisting of 22 questions, each scored by patient on a 6-point scale as follows:

- 0: No problem
- 1: Very mild problem
- 2: Mild or slight problem
- 3: Moderate problem
- 4: Severe problem
- 5: Problem as bad as it can be

The maximum total score for all symptoms is equal to 110. The total SNOT-22 scores and individual domain scores will be computed. The total score is calculated as the sum of all 22 items, and ranges from 0 to 110, with the higher scores being worse outcome. The following **Table 3** lists items and ranges for each symptom domain score.

Table 3: SNOT-22 Domain Scoring

SNOT-22 Domain	Survey Item	Score Range
Rhinologic Symptoms	1, 2, 3, 6, 21, 22	0–30
Extra-Nasal Rhinologic Symptoms	4, 5, 6	0–15
Ear/Facial Symptoms	2, 7, 8, 9, 10	0–25
Psychological Dysfunction	14, 15, 16, 17, 18, 19, 20	0–35
Sleep Dysfunction	11, 12, 13, 14, 15	0–25

9.2.4.2 RSI Questionnaire

The Rhinosinusitis Symptom Inventory (RSI) is administered using a paper (reflective) questionnaire to assess the CRS symptoms: 5 key symptoms (facial pain/pressure, facial congestion/ fullness, nasal obstruction/blockage, nasal discharge or post-nasal drip, decreased sense of smell), 7 other symptoms (headache, halitosis, dental pain, cough, ear symptoms, fevers, and fatigue) on a 6-point scale of 0 to 5, as follows:

- 0: Absent
- 1: Very mild
- 2: Mild
- 3: Moderate
- 4: Severe
- 5: Very severe

The total symptom scores and individual domain scores will be computed. The total score is calculated as the sum of all 12 symptom scores. The individual symptom scores are used to calculate 4 domain scores (**Table 4**).

Table 4: RSI Domain Scoring

RSI Domain	Symptom	Score Range
Nasal symptoms	Nasal obstruction Rhinorrea Sense of smell	0–15
Facial symptoms	Facial pain/pressure Facial congestion/fullness Headache	0–15
Otolaryngologeal symptoms	Halitosis Dental pain Cough Ear symptoms	0–20
Systemic	Fevers Fatigue	0–10

9.2.4.3 CRS Side-Specific Questionnaire

The CRS side-specific Questionnaire allows patients to evaluate each of the following 5 cardinal symptoms of CRS on the left and right side:

- Facial pain/pressure

- Facial congestion/fullness
- Nasal obstruction/blockage
- Discolored or pus nasal discharge or post-nasal drip
- Decreased sense of smell

Each side is scored individually on a 6-point scale as follows:

- 0: Absent
- 1: Very mild
- 2: Mild
- 3: Moderate
- 4: Severe
- 5: Very severe

9.2.4.4 Patient Satisfaction Questionnaire

The patient is asked to evaluate how satisfied they are with PROPEL Contour for treatment of CRS using a 5-point Likert scale as follows and whether they would recommend or not PROPEL Contour to a family member or a friend.

- Very dissatisfied
- Somewhat dissatisfied
- Neither satisfied or dissatisfied
- Somewhat satisfied
- Very satisfied

9.2.5 Implant Delivery Success

Implant delivery success is defined as successful access and deployment of the PROPEL Contour Sinus Implant into the FSO. Delivery is considered successful if the procedure concludes with correct implant placement on the intended side, even if a second attempt to place the implant is necessary. An attempted deployment occurs when the investigator introduces the delivery system into the subject's nostril with the intent of placing an implant.

9.3 Primary Efficacy Endpoint

Side-to-side difference in the FSO patency at Day 45 based on cross-sectional area of the FSO by CT measurements by an independent, blinded reviewer.

9.3.1 Definition

The cross-sectional area will be determined by the independent, blinded reviewer on CT at Day 45 within the mucosa at the location of the measured minimum diameter between 5 mm superior and 5 mm inferior to the ostium. It will be reported in mm² for the left and right ostia separately.

For each subject, the difference between FSO cross-sectional area at Day 45 in the treatment and control sides will be calculated and then averaged across all subjects in the ITT population. The FSO cross-sectional area will be set as missing if the FSO is unable to be viewed or measured.

9.3.2 Statistical Hypothesis

The primary efficacy hypothesis is that the placement of the PROPEL Contour will significantly increase the FSO cross-sectional area on the treatment side versus the control side. The relevant null and alternative hypotheses for this primary efficacy endpoint are:

$$H_0: \mu = 0$$

$$H_1: \mu \neq 0$$

Where μ represents the mean difference between the treatment and control sides in cross-sectional area of the FSO at Day 45.

9.3.3 Primary Analysis

The primary statistical method is a t-test comparing the mean FSO cross-sectional area at Day 45 in the treatment and control sides.

The study will be considered successful if there is a statistically significant difference in mean FSO cross-sectional area in favor of the treatment side. Although the alternative hypothesis is two-sided, only a statistically significant difference in average FSO area favoring the treatment side will constitute evidence of effectiveness.

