4.4 Sample Size and Power

The sample size was calculated based on the mean difference in the cross-sectional area of the FSO by CT at Day 30 between the treatment and control sides from subjects in the PROGRESS study who underwent bilateral frontal BSD followed by unilateral placement of PROPEL Contour with the following assumptions:

- Expected mean difference of 9 mm² between the treatment and control sides
- A standard deviation (SD) of 18 mm² for side-to-side difference
- Target power of 95%
- Type I error rate of $\alpha = 0.05$, 2-sided

Internal, unpublished data suggest that SD = 18 is a reasonable assumption and that an achievable difference in mean cross-sectional areas of the FSO may be greater than 9 mm². The 9 mm² is deemed to be a clinically important difference to detect. Based on standard formulas for a t-test, a sample size of 56 subjects provides at least 95% power to detect a difference of 9 mm² in mean FSO cross-sectional area between treatment side and control side. Assuming up to 20% of subjects

with non-evaluable data on one or both sides, as it was reported in PROGRESS study report (R 28020), an additional 24 subjects will be enrolled for a total of 80 randomized subjects. Sample size calculations were carried out in PASS 14 (PASS 2015).

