6.4 Role of the Independent Reviewer

The CT scans at Screening, Day 45 and 180 from all subjects will be evaluated by an independent, blinded reviewer, a role assumed by the centralized imaging core lab, for determination of the

primary and CT-related secondary efficacy endpoints. The reviewer will be independent from the study (i.e., not enrolling study subjects for the study) and blinded to implant treatment assignment (i.e., will not know which side received PROPEL Contour). CT scans will be labeled with subject ID and be provided to the independent reviewer.

The primary efficacy endpoint requires precise measurements of the FSO using reconstructed cone beam images in the axial, coronal and sagittal planes. The image reconstructions and measurements of CT-related endpoints will be performed by board-certified independent radiologists at the centralized imaging core lab in accordance with the standardized protocol (see CP-00038). The reviewers will be blinded to treatment assignment and have no access to any symptomatic or endoscopic outcomes.

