6.7 Missing Data for Efficacy and Safety Endpoints

Missing data for each efficacy endpoint will be handled as described in Sections 9.1 and 9.3.4.

For continuous endpoints, change from baseline will be set to missing at visits with missing postbaseline values or where data were imputed to missing. Continuous efficacy endpoints will be set to missing for subjects who received any of the following not allowed medication post-baseline procedure:

- Corticosteroids (e.g., oral, parenteral or injection, budesonide or other sinus steroid irrigations/rinses or drops, breath powered Xhance, nebulized steroids administered nasally or other drug eluting stents) through Day 45; or
- Biologics for CRS treatment (e.g., Dupixent).

For binary endpoints, subjects with missing efficacy data, early withdrawals, and/or subjects who received not allowed corticosteroids or biologics for chronic sinusitis condition attributable to the FSO/frontal recess will be imputed as a treatment failure. If a subject initiates high-dose steroid for other reasons not involving FSO/frontal recess, this does not represent treatment failure.

Additional rules for handling of missing data and rescue treatments are detailed below:

- *Missing efficacy data.* Visits with missing data (due to a missed visit or missing component of a composite endpoint) will be set to treatment failure.
- *Early withdrawals.* Only visits following the early withdrawal visit will be set to treatment failure.
- *Rescue treatments.* Subjects who rescue with corticosteroids (before Day 45) or biologics will be set to treatment failure at all subsequent visits and continuous endpoints set to missing.
- *Missing baseline value.* For efficacy endpoints, a missing value at baseline will not be imputed, and the endpoint will be set to missing for all visits.

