6.10 Consistency Across Study Centers

The consistency of device performance across the study centers will be investigated. A one-way analysis of variance (ANOVA) will be used to test whether the mean difference in FSO area between treatment and control sides differs by site. If a statistically significant site effect is not found (at the 0.15 significance level, i.e., $p \geq 0.15$), results will be considered poolable across sites. If a statistically significant site effect is found ($p < 0.15$), exploratory analyses will be conducted to investigate the issue. This may include regression adjustment for baseline clinical characteristics; the set of baseline characteristics to be considered include those that significantly differ across sites, or significantly predict the difference in FSO area between the treatment sides.

If regression adjustment causes the site term to become non-significant, results will be considered poolable across sites, and covariate-adjusted estimates of the treatment effect will be reported. If regression adjustment does not explain the site heterogeneity, further summaries (separating sites or excluding sites) will be explored.

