9.3.4 Sensitivity Analyses

Sensitivity analysis for medical or surgical intervention

Because intervention with oral steroids or surgical intervention may confound the primary efficacy endpoint, the following method will be applied to the analyses in cases where such interventions are performed:

- If a subject initiates oral steroids or undergoes revision ESS for CRS conditions attributable to the FSO/frontal recess before Day 45, this represents treatment failure. If the intervention occurs on the treatment side or both sides, the FSO cross-sectional area of the treatment side will be imputed with the value of the control side (i.e., side-to-side difference in FSO area is

zero). If the intervention occurs on the control side only, the FSO cross-sectional area in the control side will be imputed as zero (i.e., totally occluded).

- If a patient initiates oral steroids for other reasons not involving the FSO/frontal recess before Day 45, this does not represent treatment failure. In this scenario, the side-to-side difference in FSO cross-sectional area for that subject will be imputed as zero.
- No other data imputation rules will be applied in the planned statistical analyses.

Sensitivity analysis for missing data

Subjects with a missed visit, lost to follow-up, or with FSO cross-sectional area ‘unable to view’ by the independent, blinded reviewer will be considered as missing data. If more than 10% of the primary efficacy data are missing, the following imputation analyses will be performed to test the robustness of the primary efficacy conclusion in order:

- *Worst-case imputation.* The worst case of side-to-side difference in FSO area is zero. If the primary efficacy endpoint passes (p -value < 0.05) using worst-case imputation, then there is no need to do a best-case imputation analysis.
- *Best-case imputation.* The best case of side-to-side difference in FSO area is equal to the average for the treatment site.

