9.4 Key Secondary Endpoints

- Cross-sectional area of the FSO change from baseline to Day 45 on CT by an independent, blinded reviewer
- FSOT volume at Day 45 on CT by an independent, blinded reviewer
- FSO minimum diameter at Day 45 on CT by an independent, blinded reviewer
- Zinreich’s modified Lund-Mackay score for the frontal sinus at Day 45 on CT by an independent, blinded reviewer

- Need for post-operative intervention in the frontal recess/FSO by clinical investigators at Day 45

See Section 9.2.1 for the definitions for these endpoints.

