APPENDIX A: SCHEDULE OF ASSESSMENTS

Assessments	Screening	Baseline/ Procedure (≤ 30 d from consent date)	Day 21 (± 7 d)	Day 45 (primary endpoint) (± 7 d)	Day 90 (± 14 d)	Day 180 (end of study) (± 14 d)
Informed consent	X					
Medical/surgical history	X					
CT scan ¹	X			X		X
Endoscopic evaluation & video recording	X ²	X ²	X	X	X	X
SNOT-22 questionnaire		X ³				X
RSI questionnaire		X ³				X
CRS side-specific questionnaire		X ³	X	X	X	X
In-office bilateral frontal BSD		X				
Randomization		X				
PROPEL Contour placement in FSO ⁴		X				
Patient satisfaction questionnaire					X	X
Adverse event reporting	X	X	X	X	X	X
Device deficiency reporting		X	X	X	X	X
Concomitant medications	X	X	X	X	X	X

Abbreviations: *BSD*, balloon sinus dilation; *CT*, computed tomography; *d*, day; *FSO*, frontal sinus ostia/ostium; *RSI*, Rhinosinusitis Symptom Inventory; *SNOT*, Sino-Nasal Outcome Test.

¹ Screening CT must be performed ≤ 90 days prior to the baseline procedure to confirm the diagnosis of CRS. The follow-up CT at Day 45 and 180 shall be performed after endoscopic evaluation and debridement to ensure no implant remnants are present on the scan. All CTs should be uploaded for centralized blinded review.

² Screening endoscopic evaluation can be done at the baseline. Baseline values are entered into EDC.

³ Complete endoscopic evaluation, SNOT-22, RSI and CRS side-specific questionnaires prior to the baseline procedure. Assess implant apposition after the baseline procedure.

⁴ Treatment side only.

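### Optional: the valid primary t-test ignores the screening-CT side difference already being measured; adjusting for it narrows the interval if its correlation with Day 45 exceeds about 0.14

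*SAP*

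**What the plan says.** SAP 9.3.1 takes each subject's Day 45 FSO area on the treatment side minus the control side and averages it over the ITT population. SAP 9.3.2 tests that mean against zero, and 9.3.3 names the method: "The primary statistical method is a t-test comparing the mean FSO cross-sectional area at Day 45 in the treatment and control sides". No covariate is named. The word paired does not appear, but 9.3.1 and the sample-size input in 4.4, "A standard deviation (SD) of 18 mm² for side-to-side difference", leave no other reading.

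The screening value of the same measure is planned data. SAP 6.4 says "The CT scans at Screening, Day 45 and 180 from all subjects will be evaluated by an independent, blinded reviewer", and 9.2.1 reports area for left and right separately. The first key secondary endpoint in 9.4 depends on it: "Cross-sectional area of the FSO change from baseline to Day 45 on CT by an independent, blinded reviewer".

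The only route to a covariate-adjusted estimate is SAP 6.10. If a site test gives p < 0.15, regression adjustment may follow. Candidate covariates include those that "significantly predict the difference in FSO area between the treatment sides", and if the site term then becomes non-significant, the adjusted estimate is reported.

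Two missing-data rules bear on this. SAP 6.7 says "For efficacy endpoints, a missing value at baseline will not be imputed, and the endpoint will be set to missing for all visits". SAP 9.3.4 says "No other data imputation rules will be applied in the planned statistical analyses".

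**The concern.** Side is randomized 1:1 within subject, so the expected screening side difference is zero. A side that happened to be wider before dilation may still be wider at Day 45. That variation is noise in the unadjusted test, and a regression on the screening difference removes part of it without changing the quantity estimated or the type I error.

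As written, an adjusted estimate can arise only after a site test has been run, with covariates that may be chosen because they predict the outcome. That estimate depends on the results; a prespecified one does not.

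The change-from-baseline key secondary does not fill the gap, because subtracting the whole baseline can add more noise than it removes.

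There is also a wording problem. Read literally, the missing-baseline rule in 6.7 could discard an observed Day 45 pair for want of a screening value that the primary test does not use.

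**Working it through.** **Inputs from the documents.** Difference 9 mm², SD of the side-to-side difference 18 mm², two-sided α 0.05, 56 evaluable pairs, 80 randomized, up to 20% non-evaluable (all SAP 4.4). 80 × 0.80 = 64 pairs.

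**Assumed.** r, the correlation between screening and Day 45 side differences: 0, 0.3, 0.5, 0.7. Also 6 mm² as a smaller true effect, and k, the ratio of screening SD to Day 45 SD.

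**1. The plan's own figure.** Paired t-test, noncentral t with n − 1 df, standardized difference 9/18 = 0.5. Power first reaches 95% at n = 54 (95.02%). At n = 56 it is 95.69%, which agrees with the SAP's claim of at least 95%.

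**2. The adjusted test.** Fit D45 = a + b × Dscreen, both treatment minus control and uncentred, and test a = 0 with n − 2 df. For a given chance imbalance,

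SE(a) = 18 × √(1 − r²) × √[(1 + F/(n − 1))/n], with F distributed as F(1, n − 1).

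Averaged over F, the variance relative to the unadjusted test is (1 − r²)(n − 2)/(n − 3).

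**3. Break-even.** Setting that ratio to 1 gives |r| = 1/√(n − 2).
- 56 pairs: 1/√54 = 0.136, or 0.139 when the slightly larger t quantile is counted.
- 64 pairs: 1/√62 = 0.127, or 0.129.

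**4. Power and precision.**

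| Case | Unadjusted | r = 0 | r = 0.3 | r = 0.5 | r = 0.7 |
|---|---|---|---|---|---|
| 56 pairs, 9 mm², power % | 95.69 | 95.34 | 96.82 | 98.75 | 99.91 |
| 64 pairs, 9 mm², power % | 97.6 | 97.4 | 98.4 | 99.5 | 99.98 |
| 64 pairs, 6 mm², power % | 74.7 | 74.0 | 77.9 | 85.2 | 95.4 |
| 56 pairs, 95% CI half-width, mm² | 4.82 | 4.87 | 4.64 | 4.22 | 3.48 |

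The half-widths change by about +1, −4, −13 and −28%. The unadjusted value is 2.004 × 18/√56 = 4.82.

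**5. Validity.** In 40,000 simulated trials per setting under the null, with 56 or 64 pairs and r from 0 to 0.5, both tests rejected about 5% of the time. The covariate must not be centred at its sample mean. With centring and the usual intercept standard error, type I error at 56 pairs was about 6% at r = 0.3 and 8.7% at r = 0.5.

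**6. Change score.** Its SD is 18 × √(1 + k² − 2rk), which is below 18 only if r > k/2, so r > 0.5 when the SDs are equal. At r = 0.3 it is 17.5, 21.3 and 27.6 mm² for k = 0.5, 1 and 1.5. The residual SD from regression is 18 × √(1 − 0.09) = 17.2 mm².

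**7. Missing screening values.** With 64 pairs, r = 0.5, and 8 pairs lacking a screening difference that is set to 0 with no missing indicator, simulation gave type I error 5.0% and power at 6 mm² of 83.8% (85.2% with all values present, 74.7% unadjusted). When those 8 pairs had a true effect of 3 and the other 56 had 9, the ITT mean is (8 × 3 + 56 × 9)/64 = 8.25, and the mean estimate was about 8.24. Adding a 0/1 missing indicator would make the intercept describe only the pairs with a measured screening value, so it should be left out.

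**The case against.** The strongest reply is that nothing is broken. The t-test is valid, power exceeds 95%, and this is a choice between two sound estimators. That is right, and it is why the point is optional.

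Second, r is unknown and may be low. SAP Appendix A says "Screening CT must be performed ≤ 90 days prior to the baseline procedure to confirm the diagnosis of CRS". A bilateral dilation then alters both sides, and area is measured wherever the diameter is smallest within a 10 mm span, so the two scans need not share a plane. At r = 0.3 the interval narrows by only 4%. This stands. It limits the gain but does not make adjustment harmful.

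Third, the larger power gains use 6 mm², whereas SAP 4.4 calls 9 mm² clinically important and suggests the true difference may be greater. This also stands: at 9 mm² and r = 0.3 the gain is about one point.

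Fourth, 6.7 refers missing efficacy data to 9.1 and 9.3.4, and neither 9.3.1 nor 9.3.4 counts a missing baseline as missing primary data. The missing-baseline rule may be meant only for change scores. That is plausible, so this part needs clarifying and no more.

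Fifth, replacing a primary test late, when subjects and site staff are unblinded (protocol 19.3) and the sponsor manages the data (protocol 19.7), invites questions, and 9.3.1 and 9.3.4 would need matching edits. This is a fair argument for the supportive-analysis option.

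**Conclusion.** The point holds as an optional improvement. The planned test is valid and adequately powered. It leaves unused a covariate that the trial already measures, by the same blinded readers and on the same scale.

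Prespecified adjustment narrows the expected interval once |r| exceeds about 0.14 at 56 pairs or 0.13 at 64. The narrowing at 56 pairs is about 4% at r = 0.3 and 13% at r = 0.5. If r = 0, the interval widens by about 1% and power falls by 0.2 to 0.7 points in the cases tabulated.

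At the design effect the power gain is small. It matters more if the effect is below 9 mm² or fewer pairs are evaluable. All figures rest on SD 18 mm² and on assumed values of r.

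**What to change.** Before the blind is broken, put this in SAP 9.3.3:

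> The primary analysis regresses each subject's Day 45 FSO area difference (treatment minus control) on the screening-CT area difference (treatment minus control, not centred) and tests the intercept against 0, two-sided 0.05. The unadjusted paired t-test is supportive. If the screening difference cannot be measured, it is set to 0 with no missing indicator. This applies to the covariate only and, for the primary endpoint, overrides the missing-baseline rule of 6.7 and the line in 9.3.4 excluding other imputation.

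Make matching edits: 9.3.1 should say that the mean difference is estimated by the intercept, and 9.3.4 and 9.3.5 should say which model their analyses use.

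If the sponsor prefers to keep the t-test as primary, name this regression as the supportive analysis, with the same missing-value rule. Any adjusted estimate then no longer depends on the 6.10 site test. In that case, 6.7 should still state whether the missing-baseline rule applies to the Day 45 primary endpoint.

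The cost is SAP wording and one degree of freedom. No new data are needed.
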